6.8.1 Anticoagulation and Antibiotic Therapy

6.8.1.1 Anticoagulation Therapy

Discontinue the use of warfarin for at least three (3) days prior to the scheduled MitraClip procedure and ensure that the international normalized ratio (INR) is ≤ 1.7 prior to the MitraClip procedure. Similarly, discontinue dabigatran or factor Xa inhibitors for a sufficient duration to ensure restoration of normal coagulation. Subjects may be treated with heparin during this period at the treating physician’s discretion. If heparin is used, it should be discontinued ≥ 8 hours prior to the MitraClip procedure for subcutaneous low molecular weight heparin (LMWH) and ≥ 4 hours prior to the MitraClip procedure for intravenous unfractionated heparin (UFH).

6.8.1.2 Clopidogrel

A loading dose of clopidogrel (≥ 300 mg) is recommended within 24 hours prior to the procedure (6-24 hours prior if possible) or immediately following the procedure.

Note: A loading dose of clopidogrel may be considered even if the patient is taking clopidogrel on a daily basis either at home or in the hospital, as long as no other clopidogrel loading dose has been given within 24 hours. However, clopidogrel use is optional and its use is left to the discretion of the investigator.

Aspirin may also be used at operator discretion. If aspirin is to be used, a loading dose of 325 mg acetylsalicylic acid (ASA) may be administered either pre- or immediately post-MitraClip procedure.

6.8.1.3 Antibiotic Therapy

Administer a single dose of intravenous broad spectrum antibiotics approximately one hour prior to initiation of the procedure. The type of antibiotic is at the Investigator's discretion.

6.8.2 MitraClip Procedure

6.8.2.1 Pre-Procedural TEE

Prior to the MitraClip procedure, Device group (after randomization) and roll-in subjects must be assessed to ensure there is no significant change in subject's overall condition (e.g., stroke, MI, active infection, endocarditis, hemodynamic instability, etc. post-randomization) that would preclude treatment. If the subject has experienced any significant change that would preclude treatment, the subject must be treated and rescheduled for the MitraClip procedure as soon as possible. Subjects are required to complete an additional transesophageal (TEE) echocardiogram study within 3 days prior to the procedure to rule out the presence of intracardiac mass, thrombus or vegetation. This echocardiogram may be performed immediately preceding initiation of the MitraClip procedure. This echocardiogram will not be submitted to the ECL. If an intracardiac mass, thrombus or vegetation or other change in echocardiographic eligibility is identified in the TEE performed immediately preceding the procedure, the subject will be considered registered even if no device implant is attempted. If a thrombus is identified, the subject should be pharmacologically treated to resolve the thrombus and, if successful, the subject should be reassessed as soon as possible to undergo the MitraClip procedure. Such subjects will be considered registered even if they do not undergo the MitraClip procedure.

6.8.2.2 Pre-Procedural ECG and Physical Exam

A 12-lead ECG and physical exam should be performed within 24 hours prior to the procedure.

6.8.2.3 Baseline Activated Clotting Time

Prior to the MitraClip procedure, baseline activated clotting time (ACT) will be determined following transseptal puncture for the MitraClip procedure. ACT and heparin administration (or alternative anticoagulation therapy, e.g., bivalirudin) should be recorded.

6.8.3 Personnel

The use of transesophageal echocardiography (TEE) requires conscious sedation or general anesthesia, depending on hospital standard practice.

If complications arise during the procedure, it may be necessary to convert to an open surgical procedure. Emergency surgical back-up should be available as per the institution's standard procedures.

The Sponsor will be available to provide technical support to answer questions regarding the function and operation of the MitraClip System.

6.8.4 Subject Preparation

Subjects will be prepared for the procedure as per the institution's standard practice for a percutaneous procedure and TEE.

Note: Prior to performing the procedure, all Investigators must also undergo documented training by the Sponsor on the MitraClip System and the Clinical Investigation Plan. In addition, all Investigators must read and understand the Instructions for Use (IFU) that accompanies the Device.

Femoral vein transseptal catheterization will be completed in accordance with the IFU.

6.8.5 Anticoagulation Therapy

Following transseptal crossing, administer intravenous heparin (or alternative anticoagulation therapy, e.g., bivalirudin) in accordance with standard hospital practice. Maintain an ACT (activated clotting time) of > 250 seconds throughout the procedure. Low molecular weight heparin and fondaparinux may not be used for procedural anticoagulation.

6.8.6 MitraClip Device Placement Procedure

The Steerable Guide Catheter (Guide) is inserted into the femoral vein and advanced across the transseptal puncture. Fluoroscopic and echocardiographic guidance will be used during the procedure to visualize the devices and the vasculature and cardiac anatomy. See **APPENDIX C: Monitoring Exposure to Ionizing** for requirements for training and data gathering on ionizing radiation required per this Clinical Investigational Plan. For subjects with renal dysfunction, intravenous contrast should not be used during the procedure unless absolutely necessary.

The Guide is positioned over the mitral valve and the MitraClip Delivery System is inserted into the Guide and properly positioned over the mitral valve. The MitraClip Delivery Catheter is advanced until the MitraClip device emerges from the tip of the Guide into the left atrium. Manipulations of the catheter tip (via the control knobs on the handles) will continue in the left atrium until the MitraClip device is properly oriented perpendicular to the line of coaptation of the mitral valve. The MitraClip device is opened and advanced across the mitral valve into the ventricle then pulled back to grasp the leaflets. Two-dimensional

and/or 3-dimensional echocardiography and color flow Doppler are used to evaluate the presence of a double orifice, leaflet insertion, MitraClip device position and residual MR. If the MitraClip device is not positioned properly or MR has not been adequately reduced, additional grasping may be attempted and the MitraClip device may be inverted in the left atrium as required for additional grasping attempts. When placement is successful, the MitraClip device is closed and deployed from the Delivery Catheter. The catheters are then removed from the subject.

If placement of one MitraClip device does not result in reduction in MR to a level deemed acceptable by the operator, then a second MitraClip device may be placed to further reduce MR. The Investigator should determine if there is adequate mitral valve orifice area to accommodate the second MitraClip device without creating mitral stenosis. In most cases a maximum of two (2) MitraClip devices will be allowed to be implanted in subjects registered in this trial. However, a third MitraClip may be used in the special circumstance when one or both of the two previous MitraClip devices have detached from one leaflet or when there is evidence of inadequate MR reduction with two MitraClip devices during either the treatment visit or follow-up.

6.9 Post-MitraClip Procedure (Device Group or Roll-in Subjects)

6.9.1 Subject Management Guidelines

Immediately following the MitraClip procedure, heparin (or alternative anticoagulation therapy, e.g., bivalirudin) should be discontinued and the ACT should be monitored in accordance with hospital protocols. Vascular sheaths should be removed according to usual hospital practice.

Subjects will receive standard post-cardiac catheterization procedure care as judged appropriate by the Investigator. Subjects should be advised to limit strenuous physical activity for the first month following the MitraClip procedure or longer, as deemed appropriate by the Investigator.

6.9.2 Antibiotic Therapy

Administer additional intravenous doses of antibiotics at approximately 6 and 12 hours (or per institutional guidelines) after the completion of the procedure.

The Investigator should instruct all subjects who receive the MitraClip device of the need for endocarditis prophylaxis, as recommended in the *ACC/AHA 2008 Guideline Update on*

*Valvular Heart Disease: Focused Update on Infective Endocarditis*¹⁶. Subjects should be instructed to notify the Investigator or the subject's primary care physician in the event that a procedure recommended by this Guideline is planned, so that prophylactic antibiotics can be prescribed. A prescription for endocarditis prophylaxis may be provided to the subject at discharge.

6.9.3 Antiplatelet/Anticoagulation Regimen

Following placement of the MitraClip device, anticoagulation therapy is prescribed. If a loading dose of clopidogrel was not given prior to the MitraClip procedure, it may be administered after the procedure at investigator discretion. Post-MitraClip procedure anticoagulation is as follows:

1. Reinitiate warfarin, dabigatran or factor Xa inhibitor (if discontinued for the MitraClip procedure) at pre-procedure levels or as appropriate. If chronic oral anticoagulation is used, aspirin and clopidogrel use are not recommended, but are allowed if otherwise indicated for other conditions.
2. If chronic oral anticoagulation is not used, it is strongly recommended that either daily clopidogrel (75 mg) and/or aspirin (81 mg) is administered for 6 months or longer. If aspirin is to be used, a loading dose of 325 mg acetylsalicylic acid (ASA) may be administered either pre- or immediately post-MitraClip procedure followed by 81 mg per day for 6 months or longer at the Investigator's discretion.

6.9.4 Management of Hypertension

Subjects should have their blood pressure checked prior to discharge. Subjects should be prescribed medication as necessary following current standard of care to maintain normotensive blood pressure.

6.9.5 Vital Signs

Vital signs (i.e., weight, blood pressure, heart rate, temperature) will be obtained prior to subject discharge from the hospital.

¹⁶ Nishimura, et al. ACC/AHA 2008 Guideline Update on Valvular Heart Disease: Focused Update on Infective Endocarditis: A Report of the American College of Cardiology/American Heart Association Task Force on Practice Guidelines: Endorsed by the Society of Cardiovascular Anesthesiologists, Society for Cardiovascular Angiography and Interventions, and Society of Thoracic Surgeons. *Circulation* 2008; 118(8):887-894.

6.9.6 Implant Identification Card

At discharge, each subject implanted with a MitraClip device(s) must be provided an Implant Identification Card. An Implant Identification Card is included in the package with each MitraClip System. The subject should be instructed to keep this Implant Identification Card on their person at all times. The serial number of all implanted MitraClip device(s) should be recorded on the Implant Identification Card.

6.9.7 Procedural and Discharge Data

The following MitraClip procedural information should be recorded on the appropriate eCRF(s) after implant or attempted implant of the MitraClip device:

- General procedure information
- MitraClip implant information
- Laboratory and clinical tests
- Antiplatelet/Anticoagulation medications
- Concomitant cardiovascular medications
- Fluoroscopy duration
- Adverse events
- Protocol deviations
- Device deficiency

At the Discharge visit (Discharge occurs when subject leaves the implanting hospital), the following required tests and procedures should be completed (> 16 hours post MitraClip procedure and no later than day of discharge) as outlined below, and the information should be captured on the appropriate eCRFs:

- 12-lead ECG
- Blood draw
- Brief physical exam including vital signs (weight, heart rate, blood pressure and temperature)
- Echocardiogram (TTE) - discharge TTE must be performed at least 16 hours post MitraClip procedure and no later than 24 hours post-discharge

- Modified Rankin Scale
- Adverse events
- Protocol deviations
- Device deficiency

Instructions for the TTE are provided in this investigational plan and are located in **APPENDIX B: Echocardiography Protocol.**

6.10 “Treatment” Visit (Control Group)

The “Treatment” visit in the Control group must occur between 1 and 14 days after randomization. At the “Treatment” visit, Control group subjects will be seen by the HF specialist investigator, and will undergo a physical exam, including vital signs, cardiac health status and evaluation of heart failure medications.

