| Items | Screening/ Baseline | Randomization Assignment (For randomized Subjects only) | Treatment Visit (Control Group) | Treatment Visit (Device Group or Roll-in) | Discharge (Device Group or Roll-in) | 1-Week Phone Contact | 30-Days ^d , 6, 12, 18, 24 Months | 3, 4, 5 Years |
|--|---|--|---------------------------------------|--|--|----------------------------|---|------------------|
| Informed Consent | X | | | | | | | |
| Medical History | X within 90 days pre-registration | | | | | | | |
| Evaluation by Local Heart Team including HF Specialist Investigator and CT Surgeon Investigator (in-person consult with HF specialist and CT Surgeon investigators is required). | X within 90 days pre-registration | | X | | | | X | X |
| Components of Frailty Index | X within 14 days pre-registration | | | | | | | |
| STS Risk Score | X within 90 days pre-registration | | | | | | | |
| Modified Rankin Scale ^a | X within 14 days pre-registration | | | | X | | X not required after 12-month visit | |
| Physical Examination & Vital Signs: (height (at Baseline only), weight, heart rate, blood pressure and temperature) | X within 14 days pre-registration | | X | X within 24 hours pre- procedure | X | | X | X |
| Concomitant Cardiovascular Medications | X | | X | X | X | | X | X |
| 12-lead ECG | X within 90 days and 14 days pre- registration | | | X within 24 hours pre- procedure | X | | X | X |
| Transthoracic Echocardiogram ^b | X within 90 days pre-registration | | | | X | | X | X |

| Items | Screening/ Baseline | Randomization Assignment (For randomized Subjects only) | Treatment Visit (Control Group) | Treatment Visit (Device Group or Roll-in) | Discharge (Device Group or Roll-in) | 1-Week Phone Contact | 30-Days ^d , 6, 12, 18, 24 Months | 3, 4, 5 Years |
|---|--|--|---------------------------------------|--|--|----------------------------|---|--------------------------------------|
| Transesophageal Echocardiogram | X within 180 days pre-registration | | | X within 3 days pre- procedure | | | | |
| Albumin | X within 14 days pre-registration | | | | | | | |
| CBC with differentials and platelet count Serum Creatinine PTT or PT or INR CK, CK-MB | X within 14 days pre-registration | | | | X | | X | |
| BNP or NT-proBNP ^c | X within 90 days pre-registration | | | | | | X | |

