 - Type 3c
 - Intracranial hemorrhage (does not include microbleeds or hemorrhagic transformation, does include intraspinal)
 - Subcategories confirmed by autopsy or imaging or lumbar puncture
 - Intraocular bleed compromising vision
- Type 4: CV Surgery-related bleeding
 - Perioperative intracranial bleeding within 48 h
 - Reoperation after closure of sternotomy for the purpose of controlling bleeding

²⁰ Mehrana R, Rao SV, et al. Standardized bleeding definitions for cardiovascular clinical trials: a consensus report from the Bleeding Academic Research Consortium. *Circulation* 2011;123:2736-2747.

- Transfusion of ≥ 5 U whole blood or packed red blood cells within a 48-h period†
 - Chest tube output ≥ 2 L within a 24-h period
 - Type 5: Fatal bleeding
 - Type 5a
 - Probable fatal bleeding; no autopsy or imaging confirmation but clinically suspicious
 - Type 5b
 - Definite fatal bleeding; overt bleeding or autopsy or imaging confirmation
- *Corrected for transfusion (1 U packed red blood cells or 1 U whole blood=1 g/dL hemoglobin)
 †Cell saver products are not counted

MITRAL VALVE STENOSIS

Defined as a mitral valve orifice area of less than 1.5 cm² as measured by the Echocardiography Core Laboratory.

MODIFIED RANKIN SCALE SCORE DESCRIPTIONS

- 0: No symptoms at all
- 1: No significant disability despite symptoms; able to carry out all usual duties and activities
- 2: Slight disability; unable to carry out all previous activities, but able to look after own affairs without assistance
- 3: Moderate disability; requiring some help, but able to walk without assistance
- 4: Moderately severe disability; unable to walk without assistance and unable to attend to own bodily needs without assistance
- 5: Severe disability; bedridden, incontinent and requiring constant nursing care and attention
- 6: Dead

MITRACLIP PROCEDURE ATTEMPT

Defined as administration of anesthesia for the MitraClip procedure.

MYOCARDIAL INFARCTION

Myocardial infarction (MI) classification and criteria for diagnosis is defined as follows:

Peri-procedural MI (≤ 72 hours after MitraClip procedure)

Mandatory: CK-MB (preferred) $\geq 10x$ ULN within 72 hrs. post-MitraClip procedure in patient with normal baseline CK-MB

OR

Mandatory: CK-MB $\geq 5x$ ULN within 72 hrs. post-MitraClip procedure in patient with normal baseline CK-MB *plus* new pathological Q-waves in ≥ 2 contiguous leads, or new LBBB

Post-surgery

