Mandatory: CK-MB $\geq 10x$ ULN (preferred) within 24 hrs. of cardiothoracic surgery *plus 1 of the following*:

- New pathological Q-waves in ≥ 2 contiguous leads or new persistent LBBB on ECG ≥ 30 min. and ≤ 72 hrs. post-CABG cardiothoracic surgery, or
- New substantial wall motion abnormalities by imaging except new septal or apical abnormalities.

Spontaneous MI (>72 hours after MitraClip procedure) - this definition also applies to Control group subjects or Device group subjects who do not undergo the MitraClip procedure

Any one of the following criteria:

- Detection of rise and/or fall of cardiac biomarkers (CK-MB) with at least one value above the upper limits of normal (ULN), together with evidence of myocardial ischemia with at least one of the following:
 - ECG changes indicative of new ischemia [new ST-T changes or new left bundle branch block (LBBB)]
 - New pathological Q waves in at least two contiguous leads
 - Imaging evidence of new loss of viable myocardium or new wall motion abnormality
- Sudden, unexpected cardiac death, involving cardiac arrest, often with symptoms suggestive of myocardial ischemia, and accompanied by presumably new ST elevation, or new LBBB, and/or evidence of fresh thrombus by coronary angiography and/or at autopsy, but death occurring before blood samples could be obtained, or at a time before the appearance of cardiac biomarkers in the blood.
- Pathological findings of an acute myocardial infarction.

NEW YORK HEART ASSOCIATION CLASSIFICATION (NYHA CLASS)

| | |
|-----------|---|
| Class I | Patients with cardiac disease but without resulting limitations of physical activity. |
| Class II | Patients with cardiac disease resulting in slight limitation of physical activity. Patients are comfortable at rest. Ordinary physical activity results in fatigue, palpitation, dyspnea, or anginal pain. |
| Class III | Patients with cardiac disease resulting in marked limitation of physical activity. Patients are comfortable at rest. Less than ordinary physical activity causes fatigue, palpitation dyspnea, or anginal pain. |
| Class IV | Patients with cardiac disease resulting in inability to carry on any physical activity without discomfort. Symptoms of cardiac insufficiency or of the anginal syndrome may be present even at rest. If any physical activity is undertaken, discomfort is increased. |

NON-CARDIOVASCULAR DEATH

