#### 5.5.2 Secondary Safety Endpoints

#### 5.5.2.1 Composite 30-Day Secondary Safety Endpoint

A composite of all-cause death, stroke, MI, or non-elective (urgent or emergent) cardiovascular surgery for device related complications in the Safety Analysis Population at 30 days will be used as a secondary measure of safety. The analysis of the secondary safety endpoint is a one-group test against a performance goal for the proportion of subjects in the Safety Analysis Population free from the composite of secondary safety events at 30 days. The null and alternative hypotheses may be stated as:

$$H_0$$
:  $P_D(30) \le 0.80 \text{ vs.}$ 

$$H_1: P_D(30) > 0.80$$

where, PD(30) is the proportion of subjects free from composite of secondary safety events at 30 days in the Safety Analysis Population. This endpoint will be evaluated at the one-sided significance level of 5% with an exact test for a single proportion. The denominator of the proportion will exclude subjects in the Safety Analysis Population who terminated from the study prior to the lower window of the 30-Day visit (Day 27) without any site reported adverse events.

Components of the secondary composite safety endpoint will be summarized and reported for the Device group.

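### The only scheduled CK-MB sample that can establish a peri-procedural MI has no 72-hour limit, so in stays longer than 72 hours a compliant draw can miss the window the definition requires

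*Protocol*

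**What the plan says.** **Definition.** Protocol Appendix A sets the class as "Peri-procedural MI (≤ 72 hours after MitraClip procedure". It gives two routes. One needs CK-MB of at least 10 times the upper limit of normal. The other needs at least 5 times that limit plus new Q waves or new left bundle branch block. Both routes make CK-MB mandatory and both require the value "within 72 hrs. post-MitraClip procedure in patient with normal baseline CK-MB". The first route calls CK-MB preferred but names no alternative marker or threshold.

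**Other MI classes.** The next class is "Spontaneous MI (>72 hours after MitraClip procedure". Any one of three criteria satisfies it, and only one of the three uses CK-MB. A separate post-surgery class applies after cardiothoracic surgery.

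**Schedule.** Table 2 in Protocol 6.11 puts "CBC with differentials and platelet count Serum Creatinine PTT or PT or INR CK, CK-MB" in one row. That row is marked at screening/baseline, at discharge, and at the visits from 30 days to 24 months. It is blank for the Device group's Treatment visit and for the 1-week phone contact. Table 1 opens the 30-day visit on day 27.

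**Timing of the discharge draw.** Protocol 6.9.7 says the discharge tests "should be completed (> 16 hours post MitraClip procedure and no later than day of discharge", and that "Discharge occurs when subject leaves the implanting hospital". Length of stay is not capped.

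**Endpoint.** SAP 5.5.2.1 tests "A composite of all-cause death, stroke, MI, or non-elective (urgent or emergent) cardiovascular surgery for device related complications" against a goal of 80% event-free at 30 days. The denominator leaves out only subjects who terminate before day 27 with no site-reported adverse event. It has no rule for a subject without a CK-MB inside 72 hours.

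**The concern.** The endpoint definition and the sampling schedule are not tied together. The definition closes at 72 hours, whereas the sample that serves it closes on the day of discharge. For anyone who leaves within 72 hours the two agree automatically. For anyone who stays longer, a site can follow 6.9.7 to the letter and still have no scheduled value that could meet the definition.

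Such a subject is not recorded as unassessed. Under SAP 5.5.2.1, with no other component event, the subject enters the numerator as event-free. Any loss of this kind therefore works in one direction, towards meeting the 80% goal. SAP 5.5.2.1 also has the components summarised separately, so the MI rate is a reported result in its own right.

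**Working it through.** **1. Which scheduled samples can qualify?**

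| Scheduled CK-MB | Timing | Can it fall within 72 h after the procedure? |
|---|---|---|
| Screening/baseline | up to 14 days before registration | No, pre-procedure |
| Discharge | from >16 h to the day of discharge | Yes if drawn by 72 h; not guaranteed in longer stays |
| 30-day visit | day 27 to 44 | No |

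Only the discharge draw can qualify, and only a stay of 72 hours or less guarantees that it does.

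**2. The plan's own figure.** SAP 5.8.3.1 assumes 305 Device subjects, a 30-day MI rate of 2% and a composite rate of 12% (88% event-free), and states power above 95% at one-sided 5%. With X ~ Binomial(305, p) event-free subjects:

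- The smallest r with P(X ≥ r | p = 0.80) ≤ 0.05 is r = 256, so at most 305 − 256 = 49 events are allowed.
- Attained level: P(X ≥ 256 | 0.80) = 4.7%.
- Power: P(X ≥ 256 | 0.88) = 98.6%.

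The stated power is reproduced and is not in dispute.

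**3. Size if a share f of MIs is missed.** The documents give no value for f, so 10% to 30% is an assumption. The calculation treats the whole 2% as peri-procedural, and assumes that the missed MIs have no other component event and no clinically drawn CK-MB in the window.

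- Expected MIs: 305 × 0.02 = 6.1.
- MIs missed: 6.1 × f. Shift in the composite: 2 × f percentage points.
- Apparent freedom: true freedom + 0.02 × f.

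| f | MIs missed | Shift (points) | Chance of passing if true freedom is 80% | Power at 88% |
|---|---|---|---|---|
| 0 | 0 | 0 | 4.7% | 98.6% |
| 10% | 0.6 | 0.2 | 5.6% | 98.9% |
| 20% | 1.2 | 0.4 | 6.7% | 99.2% |
| 30% | 1.8 | 0.6 | 7.8% | 99.4% |
| 100% (bound) | 6.1 | 2.0 | 21.2% | >99.9% |

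**4. What a worst-case analysis would do.** At the planned 12%, expected events are 305 × 0.12 = 36.6, which leaves 49 − 36.6 = 12.4 before the goal is missed. Counting every otherwise event-free subject without an in-window sample as an event would thus reverse the result at about 13 such subjects. It is a bound, not an estimate.

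**The case against.** The strongest reply is that the schedule is a minimum. Appendix A accepts any CK-MB obtained within 72 hours, not only the Table 2 sample. Protocol 6.9.7 separately has laboratory and clinical tests recorded as procedural data, Protocol 8.4.1 requires adverse events found in medical records to be reported, and the Clinical Events Committee adjudicates. A patient with a difficult procedure is in hospital and can be tested on clinical grounds. This stands: the loss is possible, not certain. It does not close the gap, because none of these provisions requires a timed CK-MB, and a rise without symptoms may not prompt one.

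The other definitions also catch some cases. Two of the three spontaneous-MI criteria (sudden cardiac death with supporting findings, and pathological evidence) need no CK-MB. The biomarker criterion asks only for a value above normal, with a rise or fall and evidence of ischaemia, and an ECG and echocardiogram are required around discharge. Where onset is after 72 hours or uncertain, a late value might support that diagnosis. Post-surgical MI has its own rule, and a fatal case counts as a death in the same composite. What remains exposed is the non-fatal, non-surgical MI with onset inside 72 hours and no CK-MB in that window.

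A reader might infer that the loss is concentrated in complicated cases, where events are likeliest. The documents do not support this. Protocol 2.2.6 says only that post-procedure stays were shorter than in surgical controls, with no distribution, and clinical testing could make ascertainment better in complicated patients.

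**Conclusion.** The mismatch between the 72-hour definition and the discharge-based draw is in the text and is real for stays over 72 hours. Its effect cannot be sized from the documents, which give no length-of-stay data and no rate of clinically prompted CK-MB testing. The shift of 0.2 to 0.6 points rests on the assumed 10% to 30% and is an upper-end reading. A reader might take the same range as an estimate of how far the MI rate is understated, but that would only restate the input.

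The pass/fail decision is unlikely to change: power at the planned rate is already 98.6%. At the boundary of the goal, the chance of a false pass moves from 4.7% to between 5.6% and 7.8% under the same assumptions. The endpoint is secondary and stands last in the sequence in SAP 5.9. This is a low-severity point about ascertainment and reporting, and it does not put the composite result in doubt.

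**What to change.** 1. **Protocol 6.9.7 and Table 2.** Reconcile both with Appendix A. Require the post-procedure CK/CK-MB sample at >16 hours and no later than 72 hours after the procedure, or at discharge if that is earlier, and record the draw time.
2. **SAP 5.5.2.1, reporting.** Give the number of subjects in the Safety Analysis population with no CK-MB within 72 hours.
3. **SAP 5.5.2.1, sensitivity.** Exclude from the denominator those among them who have no other component event. As a worst case, count them as events. Both analyses lean against the device, since they remove or reverse only subjects otherwise counted as event-free, so they should be labelled as bounds beside the primary test.

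**Cost.** CK-MB shares a row with the blood count, creatinine and coagulation tests. Long-stay subjects would either have the whole row drawn earlier, giving up those values near discharge, or have one additional blood tube. The SAP changes are one count and two short analyses. If sampling is already complete, items 2 and 3 can still be done wherever draw times can be recovered.
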